**Table H1. Infusion Reaction Treatment Guidelines for Pembrolizumab**

- **Overdose:** An overdose that is not associated with clinical symptoms or abnormal laboratory results.

For purposes of this trial, an overdose of pembrolizumab will be defined as any dose of 1,000 mg or greater ( $\geq 5$  times the indicated dose). No specific information is available on the treatment of overdose of pembrolizumab. Appropriate supportive treatment should be provided if clinically indicated. In the event of overdose, the subject should be observed closely for signs of toxicity. Appropriate supportive treatment should be provided if clinically indicated.

If an adverse event(s) is *associated with* (“results from”) the overdose of a Merck product, the adverse event(s) is reported as a serious adverse event, even if no other seriousness criteria are met.

If a dose of Merck’s product meeting the protocol definition of overdose is taken *without* any associated clinical symptoms or abnormal laboratory results, the overdose is reported as a non-serious Event of Clinical Interest (ECI), using the terminology “accidental or intentional overdose without adverse effect.”

**REFERENCE:** Merck. *Pembrolizumab Program (MK-3475) Event of Clinical Interest Guidance Document*. Version 5.0. 18-Dec-2014.

## **APPENDIX I: PATIENT DOSING DIARY AND BLOOD PRESSURE LOG FOR AXITINIB**

*[Note to Investigators: This appendix consists of a “directions sheet and diary” to be handed to the patient prior to each cycle. These sheets MUST be approved by the Institutional Review Board (IRB) before it may be given to patients.]*

### Diary Directions

Begin taking axitinib twice a day, (as your doctor has told you to during the study):

1. On the days that you are supposed to take axitinib – axitinib should be taken by mouth, twice a day on an empty stomach, approximately 12 hours apart with a glass of water.
2. You may take each dose with or without food. Do not chew or break tablets.
3. If a dose is missed you may take the missed dose if it has been less than 2 hours from your scheduled dose. Do not make up missed doses if it has been more than 2 hours from your scheduled dose.
4. If you vomit after a dose, do not take another dose. Take your next dose of the day at the same time you would normally take it.
5. Avoid taking grapefruit juice and St. John’s Wort.
6. Avoid smoking if you are taking axitinib because it may decrease the amount of the drug in your body.
7. Taking over-the-counter drugs to block stomach acid may interfere with the absorption of the study drug. Please avoid taking medications like omeprazole (Prilosec OTC) or cimetidine (Tagamet) unless you first discuss with your doctor.
8. Please bring the empty bottle or any leftover tablets and this diary to your next clinic visit.

**Patient Dosing Diary** Axitinib Dose Level: \_\_\_\_\_ mg twice a day  
**Patient Initials (L, F, M): Patient ID:** \_\_\_\_\_ **Cycle:** \_\_\_\_\_

This is a diary on which you are to **record the date, time and number of tablets you take each day on the days that you are supposed to take Axitinib**. You should take your scheduled dose of each tablet. If you forget to take a dose, please write "0", but remember to take your prescribed dose at the next regularly scheduled time.

Day	Date(s)	# of Tablets	Time Taken (Circle AM or PM)	# of Tablets	Time Taken (Circle AM or PM)
1			AM PM		AM PM
2			AM PM		AM PM
3			AM PM		AM PM
4			AM PM		AM PM
5			AM PM		AM PM
6			AM PM		AM PM
7			AM PM		AM PM
8			AM PM		AM PM
9			AM PM		AM PM
10			AM PM		AM PM
11			AM PM		AM PM
12			AM PM		AM PM
13			AM PM		AM PM
14			AM PM		AM PM
15			AM PM		AM PM
16			AM PM		AM PM
17			AM PM		AM PM
18			AM PM		AM PM
19			AM		AM

			PM		PM
20			AM PM		AM PM
21			AM PM		AM PM
22			AM PM		AM PM
23			AM PM		AM PM
24			AM PM		AM PM
25			AM PM		AM PM
26			AM PM		AM PM
27			AM PM		AM PM
28			AM PM		AM PM
29			AM PM		AM PM
30			AM PM		AM PM
31			AM PM		AM PM
32			AM PM		AM PM
33			AM PM		AM PM
34			AM PM		AM PM
35			AM PM		AM PM
36			AM PM		AM PM
37			AM PM		AM PM
38			AM PM		AM PM
39			AM PM		AM PM
40			AM PM		AM PM
41			AM PM		AM PM

Days 42 to 49 below are ONLY to be completed for Cycle 1 of axitinib; After Cycle 1: Do NOT take axitinib nor complete Days 42 to 49.					
42			AM		AM
			PM		PM
43			AM		AM
			PM		PM
44			AM		AM
			PM		PM
45			AM		AM
			PM		PM
46			AM		AM
			PM		PM
47			AM		AM
			PM		PM
48			AM		AM
			PM		PM
49			AM		AM
			PM		PM

**Patient Signature:** \_\_\_\_\_

**Date:** \_\_\_\_\_

	am			 Yes	 No	am		
	pm			 Yes	 No	pm		
	am			 Yes	 No	am		
	pm			 Yes	 No	pm		
	am			 Yes	 No	am		
	pm			 Yes	 No	pm		
	am			 Yes	 No	am		
	pm			 Yes	 No	pm		
	am			 Yes	 No	am		
	pm			 Yes	 No	pm		
	am			 Yes	 No	am		
	pm			 Yes	 No	pm		
	am			 Yes	 No	am		
	pm			 Yes	 No	pm		
	am			 Yes	 No	am		
	pm			 Yes	 No	pm		
	am			 Yes	 No	am		
	pm			 Yes	 No	pm		
	am			 Yes	 No	am		
	pm			 Yes	 No	pm		

**Patient Signature:** \_\_\_\_\_

**Date:** \_\_\_\_\_

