### PROTOCOL SCHEMA

The first cycle of treatment will be seven weeks, with one week of axitinib alone prior to initiation of pembrolizumab. Subsequently, six-week cycles of treatment consist of twice daily oral doses of axitinib administered continuously with intravenous (I.V.) administration of pembrolizumab on day 1 and 22. The first five evaluable patients will be considered a safety lead-in, and will not have axitinib dose escalation above 5 mg PO bid. In subsequent cycles, patients will begin cycle 1 with axitinib 5 mg PO twice daily (BID) and be monitored for DLT; these patients may then have axitinib dose-escalated as tolerated for the individual patient starting with cycle 2. Dose de-escalations may occur at any time for toxicity.

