### 7.2 Dose-Limiting Toxicity (DLT)

Dose-Limiting Toxicity (DLT) is defined as any one of the following Adverse Events (AEs) that occurs during the first cycle (49 days) and is considered by the Investigator to be related (possible, probable, or definite) to study drug, specifying attribution to axitinib, pembrolizumab, or both. Management and dose modifications associated with the above AEs are outlined in Section 10.0 (Treatment/Dose Modifications).

DLT is defined as any one of the following (Table 4 and 5):

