**Table 5. Summary of Non-Lab DLTs.**

### 8.0 TREATMENT PLAN

A cycle of treatment will consist of concurrent axitinib and pembrolizumab therapy for 6 weeks (Figure 3, Table 6), except for cycle 1 which will be 7 weeks as detailed above. Administration of axitinib shall occur continuously with pembrolizumab administered on day 8 and day 29 of the first cycle, and days 1 and 22 of the following cycles. The first five patients will not be dose-escalated above 5 mg PO twice daily axitinib. If these patients exhibit acceptable rates of DLT, starting with patient 6, dose-escalation of axitinib will be permitted. No dose escalations will be permitted during cycle 1. On day 1 of cycle 2 and the subsequent cycles, dose escalation of axitinib is permitted if toxicity is within the specified criteria. No dose-escalation will be conducted in the middle of any cycle. Dose reduction or interruption is permitted in the case of toxicity at any time as per section 10.0.

Trial treatment should be administered after all procedures/assessments have been completed as detailed in Section 12.0. Trial treatment may be administered up to 3 days before or after the scheduled Day 1 of each cycle due to administrative (e.g. scheduling) reasons.

Cycle(s)	1							2						Imaging prior to every subsequent odd cycle (i.e. 3, 5, 7, 9, etc.)	3, 4, 5, etc. until progression					
	1	2	3	4	5	6	7	1	2	3	4	5	6		1	2	3	4	5	6
Week(s)	1	8	1	2	2	3	4	1	8	1	2	2	36	1	8	1	2	2	3	
Day(s)	1	8	5	2	9	6	3	1	8	5	2	9	36	1	8	5	2	9	6	
Axitinib oral, BID continuously (uptitration permitted starting from cycle 2)	X	X	X	X	X	X	X	X	X	X	X	X	X	X	X	X	X	X	X	
Pembrolizumab IV q21 days		X			X			X			X			X			X			

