**Table 7. Treatment Schema: Axitinib Monotherapy**

For patients who progress while on axitinib monotherapy, pembrolizumab can be re-introduced and patients can be treated with the axitinib/pembrolizumab combination treatment for up to 17 additional cycles (approximately 1 year). A cycle of treatment will consist of axitinib/pembrolizumab combination therapy for 6 weeks (Table 8). Administration of axitinib shall occur continuously with pembrolizumab administered on days 1 and 22.

Once participants complete the additional year of axitinib/pembrolizumab treatment, they will continue with axitinib monotherapy indefinitely until they experience toxicity, withdrawal or consent, or as per the treating physician’s discretion. The indefinite axitinib monotherapy treatment schema will be the same as for the axitinib monotherapy (Table 7).

Cycle(s)	1, 2, 3, etc. up to 17 cycles (approximately 1 year)						Imaging prior to every subsequent odd cycle (i.e. 3, 5, 7, 9, etc.)
Week(s)	1	2	3	4	5	6	
Day(s)	1	8	15	22	29	36	
Axitinib oral, BID continuously	X	X	X	X	X	X	
Pembrolizumab IV q21 days	X			X			

**Table 8. Treatment Schema: Axitinib/Pembrolizumab Combination Treatment for Patients who Progress while on Axitinib Monotherapy**

				First 2 years of combination Axitinib/Pembrolizumab treatment		Axitinib Monotherapy (until progression) ***		Combination Axitinib/Pembrolizumab treatment (Additional Year)	
Agent	Premedications & Precautions	Dose	Route	Schedule	Cycle Length* *	Schedule	Cycle Length	Schedule	Cycle Length
Axitinib	Premedicate with ondansetron 8 mg orally if needed for nausea  Take daily doses 12 hours apart and swallow whole with or without food with a glass of water	* 5mg	PO BID	** Days 1-42 (week 1-6)	42 days (6 weeks) **	Days 1-84 (week 1-12)	84 days (12 weeks)	** Days 1-42 (week 1-6)	42 days (6 weeks) **
Pembrolizumab	Monitor for infusion reactions with hypersensitivity kit at bedside.  Grade 2 infusion reactions will be premedicated with diphenhydramine 50 mg IV and acetaminophen 1000 mg PO prior to subsequent infusions.  Diet: Subjects should maintain a normal diet unless modifications are required to manage an AE such as diarrhea, nausea or vomiting.	200 mg	IV infusion over 30 minutes (-5min/+10min)	Cycle 1: Day 8, 29  Subsequent cycles: Day 1, 22		NA	NA	Each Cycle: Day 1, 22	

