### 8.5.1 Axitinib

During the first two years of axitinib/pembrolizumab combination treatment, eligible patients will be dispensed the appropriate number of axitinib tablets required for at least 21 days of dosing plus an additional 3-day supply to account for visit scheduling.

Once participants have completed the first two years of axitinib/pembrolizumab combination treatment, eligible patients will be treated with axitinib monotherapy until progression. During this time, eligible patients will be dispensed the appropriate number of axitinib tablets required for at least 84 days of dosing plus an additional 3-day supply to account for visit scheduling.

Pembrolizumab will be re-introduced for participants who progress while being treated with axitinib monotherapy. Eligible patients will be dispensed the appropriate number of axitinib tablets required for at least 21 days of dosing plus an additional 3-day supply to account for visit scheduling.

Once participants complete the additional year of axitinib/pembrolizumab treatment, they will continue with axitinib monotherapy indefinitely until they experience toxicity, withdrawal or consent, or as per the treating physician's discretion. During this time, eligible patients will be dispensed the appropriate number of axitinib tablets required for at least 84 days of dosing plus an additional 3-day supply to account for visit scheduling.

Treatment compliance will be assessed based on return of unused axitinib tablets and a dosing diary. Eligible patients will be given a dosing diary for each treatment cycle. Date, time, and dose should be recorded at each dosing time point to confirm that each BID dose of axitinib was taken for each day.

The medication diary will be reviewed weekly during each week of axitinib administration (at a minimum during the first 3 weeks of each cycle, or otherwise noted) and returned to clinic staff at the end of each cycle. See Appendix I for the dosing diary. During the first cycle of axitinib, or for the first three weeks after any dose escalation or reduction of axitinib, patients will also be asked to record their blood pressure at least once each day before their evening dose of axitinib. See also Appendix I for the blood pressure diary.

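### After cycle 1, the Appendix I diary tells patients not to take or record axitinib on day 42, which the protocol schedules as a dosing day

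*Combined protocol and SAP*

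**What the plan says.** **Dosing schedule.** The Protocol Schema states that, after cycle 1, "six-week cycles of treatment consist of twice daily oral doses of axitinib administered continuously". Section 8.0 repeats that "Administration of axitinib shall occur continuously" and places pembrolizumab on days 1 and 22 of these later cycles. Table 9 gives the axitinib schedule for a 42-day combination cycle as "Days 1-42 (week 1-6". Its footnote makes cycle 1 the exception, at seven weeks, because a week of axitinib alone comes first. Section 7.2 gives the length of cycle 1 as 49 days.

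**Diary.** Appendix I is a directions sheet and diary "to be handed to the patient prior to each cycle". Rows 1 to 41 are open in every cycle. A line printed above row 42 reserves rows 42 to 49 for cycle 1 and continues: "After Cycle 1: Do NOT take axitinib nor complete Days 42 to 49". Under Section 8.5.1 each cycle has its own diary, and compliance is judged from the diary together with returned tablets.

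**The concern.** The two instructions conflict on day 42. The treatment plan makes it a dosing day in every six-week combination cycle. After cycle 1, the diary tells the patient to skip it.

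This is an operative dosing instruction on a sheet the patient takes home, so it can change what is swallowed. It also affects the record. A patient who correctly takes axitinib on day 42 is told to leave that row blank, although the diary is meant to document each twice-daily dose. The stakes are one day of drug and one day of compliance data per later cycle.

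**Working it through.** No sample-size or power formula applies; the check is a day count.

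**Inputs**
- Length of later combination cycles: 42 days (Table 9; six weeks in the Protocol Schema and Section 8.0).
- Length of cycle 1: 49 days (Section 7.2; seven weeks in the Table 9 footnote).
- Axitinib: twice daily, continuous (Protocol Schema, Section 8.0).
- Pembrolizumab: days 1 and 22 after cycle 1 (Section 8.0), every 21 days (Section 8.4).
- Diary rows reserved for cycle 1: 42 to 49 (Appendix I).

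**Step 1. Reproduce the stated cycle lengths.** 6 × 7 = 42 days and 7 × 7 = 49 days, as stated. The pembrolizumab schedule agrees: 22 + 21 = 43, so day 43 is the next Day 1 and day 42 is the last day of the current cycle.

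**Step 2. Count the days that belong only to cycle 1.** 49 − 42 = 7 days, which are days 43 to 49. The diary reserves 49 − 42 + 1 = 8 rows. The surplus row is day 42.

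**Step 3. Count the scheduled doses barred if the sheet is followed literally.** The protocol schedules 42 × 2 = 84 doses in a later cycle. The diary allows 41 × 2 = 82. The difference is 2 doses, and 2/84 = 2.4%.

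| Situation | Next Day 1 falls on | Scheduled doses barred |
|---|---|---|
| Cycle 1 | day 50 | 0 of 98 |
| Later cycle, next Day 1 on schedule | day 43 | 2 of 84 (2.4%) |
| Later cycle, next Day 1 is 1 to 3 days early | day 42, 41 or 40 | 0 |

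In the last row the new cycle has begun by the time day 42 would have come.

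**Step 4. Compare with the 80% rule.** Sections 3.1 and 16.2 require 80% of scheduled axitinib doses but do not say over what period. Any period that runs from the start of treatment to the end of cycle n, with visits on schedule, loses 2(n − 1) of 98 + 84(n − 1) doses. For n = 1 this is 0. For n = 2 it is 2/182 = 1.1%. As n grows it approaches 2/84 = 2.4% from below. The rule tolerates a 20% shortfall, so whichever of these periods is meant, the diary error alone cannot take a patient below it.

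**The case against.** The strongest case on the other side is that this is a one-row slip with little consequence. Patients are told to take axitinib as their doctor directs, the study team sees the diary at visits, and leftover tablets are returned and counted. No endpoint, estimate or stopping boundary depends on day 42. The last part stands in full. The safeguards count for less: diary collection and tablet counts at the next Day 1 come after the doses have been missed, and a general direction to follow the doctor does not clearly override a capitalised prohibition. Verbal advice may well prevent the error in practice, and the documents cannot show how often.

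Two stronger readings are tempting.

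- **Late visits.** Section 8.0 says: "Trial treatment may be administered up to 3 days before or after the scheduled Day 1 of each cycle". Section 8.5.1 dispenses the tablets "required for at least 21 days of dosing plus an additional 3-day supply to account for visit scheduling". A reader might infer that a patient whose next Day 1 is three days late should dose on days 43 to 45 as well, so that the diary bars days 42 to 45, or 8 of (42 + 3) × 2 = 90 doses (8.9%). Continuous dosing makes that plausible, but the documents do not establish it. Table 9 stops at day 42, the window concerns when treatment is given around Day 1, and the reserve is a supply rule. No text says how days after 42 are to be dosed, or whether a late patient stays on the old diary.
- **Monotherapy.** A reader might also infer that the same sheet misdirects patients in the 84-day axitinib cycles. Nothing shows that it is used there. Section 12.2 calls for the diary appropriate to each treatment cycle.

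**Conclusion.** The error is real and confined to one day. The cycle-1-only block in Appendix I should start at day 43 and starts at day 42. No other text in the protocol corrects it, and no planned axitinib-free day was found that could explain it.

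The size is 2 of 84 scheduled doses (2.4%), withheld and unrecorded, in each later six-week combination cycle. That figure assumes that the patient follows the printed line literally and that the next Day 1 is on schedule. It is the most the sheet could cost under those conditions and does not estimate what was lost.

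It would be wrong to infer a threat to evaluability or to the progression-free survival result. The shortfall is far inside the 20% allowance, and cycle 1, which is the DLT window, is untouched. Severity is low. The correction is worth making because the sheet contradicts the treatment plan in every later six-week combination cycle and the remedy is simple.

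**What to change.** In Appendix I:

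1. Move row 42 above the restricted block, so that it is dosed and recorded in every six-week cycle.
2. Change both mentions of Days 42 to 49 to Days 43 to 49.
3. Label the block as belonging to the first, seven-week combination cycle. Cycle numbering restarts at 1 when pembrolizumab is re-introduced, and Table 8 shows those cycles as six weeks, so a bare cycle 1 label could mislead.

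How to dose and record when the next Day 1 falls late is a separate matter that the documents leave open. This correction neither needs nor settles it.

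The cost is a reprint of the diary with IRB approval. The protocol body and the analysis do not change.

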**APPENDIX J: CYP1A2, CYP2C8, CYP2C19, CYP3A4 SUBSTRATES, INHIBITORS & INDUCERS \***

SUBSTRATE(S)				
1A2	2C8	2C19	3A4	
amitriptyline caffeine clomipramine clozapine cyclobenzaprine duloxetine estradiol fluvoxamine haloperidol imipramine N-DeMe mexiletine naproxen olanzapine ondansetron phenacetin→ acetaminophen→NAP QI propranolol riluzole ropivacaine tacrine theophylline tizanidine triamterene verapamil (R)warfarin zileuton zolmitriptan	[paclitaxel] torsemide amodiaquine cerivastatin repaglinide sorafenib	Proton Pump Inhibitors (PPIs): esomeprazole lansoprazole omeprazole pantoprazole rabeprazole  Anti-epileptics: diazepam→Nor phenytoin(O) S-mephenytoin phenobarbitone  amitriptyline carisoprodol citalopram chloramphenicol clomipramine chlopidogrel cyclophosphamide hexobarbital imipramine N-DeMe indomethacin labetalol R-mephobarbital moclobemide nelfinavir nilutamide primidone progesterone proguanil propranolol teniposide R-warfarin→8-OH voriconazole	Macrolide antibiotics: clarithromycin erythromycin (not 3A5) NOT azithromycin telithromycin  Anti-arrhythmics: quinidine→3OH (not 3A5)  Benzodiazepines: alprazolam diazepam→3OH midazolam triazolam  Immune Modulators: cyclosporine tacrolimus (FK506)  HIV Antivirals: indinavir nelfinavir ritonavir saquinavir  Prokinetic: cisapride  Antihistamines: astemizole chlorpheniramine terfenadine  Calcium Channel Blockers: amlodipine diltiazem felodipine lercanidipine nifedipine nisoldipine nitrendipine verapamil  HMG CoA Reductase Inhibitors: atorvastatin cerivastatin	Steroid 6beta-OH: estradiol hydrocortisone progesterone testosterone  Miscellaneous: alfentanil aprepitant aripiprazole boceprevir buspirone carbamazepine cafergot caffeine→TMU cilostazol cocaine codeine-N-demethylation dapsone dexamethasone dextromethorphan docetaxel domperidone eplerenone fentanyl finasteride gleevec haloperidol irinotecan LAAM lidocaine methadone nateglinide nevirapine ondansetron pimozide propranolol quetiapine quinine risperidone romidepsin NOT rosuvastatin salmeterol sildenafil sirolimus sorafenib

SUBSTRATE(S)			
1A2	2C8	2C19	3A4
			lovastatin NOT pravastatin NOT rosuvastatin simvastatin  tamoxifen taxol telaprevir terfenadine torisel trazodone vemurafenib vincristine zaleplon ziprasidone zolpidem

INHIBITORS			
1A2	2C8	2C19	3A4
fluvoxamine ciprofloxacin cimetidine amiodarone efavirenz fluoroquinolones fluvoxamine furafylline interferon methoxsalen mibefradil ticlopidine	gemfibrozil trimethoprim glitazones montelukast quercetin	PPIs: Esomeprazole lansoprazole omeprazole pantoprazole  Other: rabeprazole chloramphenicol cimetidine felbamate fluoxetine fluvoxamine indomethacin ketoconazole modafinil oral contraceptives oxcarbazepine probenecid ticlopidine topiramate voriconazole	HIV Antivirals: indinavir nelfinavir ritonavir clarithromycin itraconazole ketoconazole nefazodone saquinavir telithromycin aprepitant erythromycin fluconazole grapefruit juice verapamil diltiazem cimetidine amiodarone NOT azithromycin Chloramphenicol boceprevir ciprofloxacin delaviridine diethyldithiocarbamate fluvoxamine gestodene imatinib mibefradil mifepristone norfloxacin norfluoxetine star fruit telaprevir voriconazole

INDUCERS			
1A2	2C8	2C19	3A4
broccoli brussel sprouts carbamazepine char-grilled meat insulin methylcholanthrene modafinil nafcillin beta-naphthoflavone omeprazole rifampin tobacco	rifampin	carbamazepine nevirapine phenobarbital rifampin secobarbital St. John's Wort	HIV Antivirals: efavirenz nevirapine barbiturates carbamazepine glucocorticoids modafinil oxcarbazepine phenobarbital phenytoin pioglitazone rifabutin rifampin St. John's wort troglitazone

\*Reference: <http://medicine.iupui.edu/clinpharm/ddis/main-table/>

## **APPENDIX K: GUIDELINES FOR PREPARATION AND ADMINISTRATION/ KEYTRUDA FOR INJECTION (LYOPHILIZED POWDER)**

### *Reconstitution of Keytruda for Injection (Lyophilized Powder)*

- Add 2.3 mL of Sterile Water for Injection, USP by injecting the water along the walls of the vial and not directly on the lyophilized powder (resulting concentration 25 mg/mL).
- Slowly swirl the vial. Allow up to 5 minutes for the bubbles to clear. Do not shake the vial.

